### **1. Background and Significance**

**Cardiac arrest (CA) is a heart AND brain problem that produces cognitive, physical, and emotional challenges.** Because the whole brain is deprived of oxygen from the heart stopping, cardiac arrest (CA) survivors with “good neurologic recovery” (i.e., cognitively intact) still experience broad cognitive sequelae (e.g., changes in memory, attention, visuospatial abilities, language, and executive functions) and physical sequelae (e.g., loss of motor functions, fatigue, weakness, and chronic pain from the rescue compressions). Little attention is paid to these “extracardiac” sequelae, which become chronic and distressing. Unsurprisingly, up to 61% of CA survivors and 40% of caregivers develop clinically significant emotional distress (posttraumatic stress, anxiety, and depression).

**CA is a complete mind-body-heart disruption that is continuously traumatic.** Through qualitative interviews, we have shown that CA survivors experience *enduring somatic threats* (recurring, somatic traumatic reminders of their event), including the sensation of their implantable cardioverter defibrillator (ICD) inside their chest, invasive electrical shocks discharged from the ICD, and the cognitive and physical sequelae listed above. These enduring somatic threats remind survivors of their mind-body-heart disruption and prevent them from living fully in the present. Furthermore, lingering memory and cognitive changes contribute to confusion, fear, and self-doubt. Other daily stressors include hyperarousal of future cardiac events, emotional numbing, and existential distress. Informal caregivers witness (and remember) the CA event, graphic rescue interventions, intensive care unit (ICU) stay, and lengthy, variable recovery. Because reminders of the event are recurring, the emotional symptoms can linger for up to 10 years.

**Emotional distress post-CA undermines QoL and leads to premature morbidity and mortality.** In CA survivors and caregivers, we have shown that 1) emotional distress is the strongest predictor of QoL and subjective recovery and 2) in survivors, elevated emotional distress is linked to a greater likelihood of adverse events and mortality at 1-year post-discharge. In short, emotional distress compromises both the quality and length of CA survivorship.

**CA survivors and caregivers lack resources to navigate survivorship, which exacerbates emotional distress.** Unlike other critical illnesses such as stroke or myocardial infarction, there is no “standardized pathway” for follow-up care post-CA. Further, there is no reliable provision of resources to survivors and caregivers needed to manage survivorship. Consequently, CA survivors and caregivers are left without

direction, unable to manage the broad post-CA sequelae. In a recent survey of ours, only ~8% of CA survivors reported receiving appropriate cognitive or emotional support resources. As a result, survivors and caregivers are unprepared to navigate the health system, which exacerbates their emotional distress.

**There are currently no psychosocial interventions for CA survivors or caregivers in the United States.** In 2020 the AHA called for the development of psychosocial interventions and reliable resource provision for CA survivors and caregivers. However, there are still no psychosocial interventions for the CA population. Developing a psychosocial intervention that also provides resources for CA survivors and caregivers is innovative and necessary. CA survival continues to improve, meaning there is a growing population of survivors and caregivers in need of services.

**A dyadic mind-body intervention is best suited to address emotional distress in CA survivors and caregivers.** CA survivors often depend on a caregiver for emotional and functional support. Caring for both survivors and caregivers leads to overall better adjustment for both dyad members. Caregivers cannot fully care for the survivor if they themselves are distressed. Mind-body skills (e.g., mindfulness, meditation, relaxation, progressive muscle relaxation, body scanning) are effective in reducing the emotional symptoms experienced by CA survivors and their caregivers (i.e., hyperarousal, numbing, existential distress). These symptoms actively or passively remove one from the present, whereas mind-body skills keep one fully in the present. Our preliminary data supports the application of these skills post-CA: 1) greater use of mindfulness skills was associated with less emotional distress in long-term CA survivors 2) CA survivors reported that mindfulness and meditation were amongst their most important coping strategies.

**We plan to develop a dyadic mind-body intervention for CA survivors with good neurologic recovery and their caregivers at-risk for chronic emotional distress.** A dyadic-mind body intervention delivered early post-CA is ideal for four main reasons: **First**, untreated emotional distress post-CA becomes chronic, with detrimental impacts on QoL and disease burden. **Second**, mind-body skills are interdependent (the skills of one dyad member influence the other member). A successful dyadic intervention can lead to synergistic positive effects in both the survivor and caregiver. **Third**, the specific emotional symptoms exhibited by survivors and caregivers can be effectively treated by mind-body techniques. **Fourth**, our intervention will provide resources to help navigate survivorship, which is a major treatment gap in this population.

## 2. Specific Aims and Objectives

**Aim 1: Refine RT-CA.** We will conduct a single-arm open pilot of RT-CA (N=5 dyads) to evaluate initial feasibility and acceptability using exit interviews and pre-post assessments.

Findings from Aim 1 will then inform the next iteration of the RT-CA manual and feasibility trial.

**Aim 2: Conduct medical record review** of all admitted cardiac arrest patients at MGH during the study period (N = 200-400). We will collect basic cardiac arrest clinical data on these patients to determine the representativeness of our sample in Aim 1 to all cardiac arrest admissions at MGH and the United States.

Findings from Aim will inform recruitment gaps, if any, and contextualize the recruitment pool at MGH relative to the United States.

## 3. General Description of Study Design

We are proposing an open pilot trial of RT-CA with 5 CA survivor-caregiver dyads. All dyads will undergo the 6-session intervention. The first session will be at the bedside (unless the survivor is discharged before session 1 takes place, at which point we will meet over Zoom or telephone (Doximity)). The remaining sessions will be conducted over Zoom or telephone (Doximity) depending on participant preference.

Parallel to our open pilot, we propose to conduct medical record of all admitted cardiac arrest patients at MGH during the study period and maintain them in a study log (N = 100-300). As part of our recruitment efforts (see sections 4 and 5), we will pre-screen Epic ICU and stepdown floor rosters in order to identify all cardiac arrest patient admissions, who could be eligible for our open pilot. By including all admissions into a study log we will be able to 1) monitor cardiac arrest patients' mental status during their hospital stay to see if they will become eligible for our open pilot and 2) determine the representativeness of the open pilot sample's cardiac arrest clinical characteristics.

We will need to access the medical records of all cardiac arrest admissions to monitor them throughout their stay in the hospital. If the patient recovers good neurological status, they may be eligible for our study, at which point we will follow our recruitment and enrollment procedures as detailed below. There is no guarantee that a patient with cardiac arrest recovers neurological status, so we will need to conduct daily pre-screening of their neurological exam until they become potentially eligible or are discharged.

Additionally, we will need to collect basic cardiac arrest clinical data of all cardiac arrest admissions in order to contextualize our study sample in the context of cardiac arrest admissions at MGH and the US overall. This information is routinely collected and reported in cardiac arrest research. We will need to be able to identify if our enrolled sample is representative of the greater population, and if not, we will need to report the disparities that exist in our enrolled sample.

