#### **4. Subject Selection**

We will recruit and enroll dyads from MGH ICUs and stepdown floors. The majority of cardiac arrest (CA) survivors are initially cared for in the Heart Center Intensive Care Units and stepdown floors, while a minority are also cared for in the Neuro-ICU, Medical Intensive Care Unit, and Cardiac Surgical Intensive Care Unit, and corresponding stepdown floors.

During phase 1 of this study, the PI presented to staff from these ICUs and stepdown floors that care for CA survivors on the overall study aims, purpose, potential benefits to participants, and best ways to facilitate referrals.

Trained study staff will identify new CA survivors primarily through daily pre-screening of ICU and stepdown survivor rosters. We will also obtain referrals from the medical, nursing, or social work team members that are clinically caring for survivors and caregivers on service, whom the PI presented to during phase 1 of the overall study. A new CA survivor is defined as any survivor with a new diagnosis of "cardiac arrest" and documented loss of pulse in their medical record. Study staff will always confirm with a clinical team member about whether screened survivors might be appropriate study candidates before approaching to discuss our study.

Through pre-screening of ICU and stepdown floor patient rosters on Epic, our research assistant (RA) will identify CA survivors and add them to a "cardiac arrest admissions log" stored on REDCap of all CA survivors admitted to MGH during the study period. The cardiac arrest admissions log will serve to aid the RA in monitoring all currently admitted CA survivors' neurological exams to see if they will become eligible for the study. Specifically, the RA will conduct daily review of all currently admitted CA survivors' neurological exam daily as documented in the electronic medical record. The RA will specifically attend to the survivor's documented alertness, orientation, and speech output. The majority of cardiac arrest

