admissions will not regain sufficient neurological function to participate in our open pilot, however, we will keep their basic clinical cardiac arrest characteristics in the admissions log for the duration of the study so that we can then compare our open pilot sample's characteristics to the characteristics of cardiac arrest admissions at MGH, and compare the cardiac arrest admissions at MGH to cardiac arrest patients in the United States. This information is routinely collected and reported in cardiac arrest research. We will need to be able to identify if our enrolled sample is representative of the greater population, and if not, we will need to report the disparities that exist in our enrolled sample.

Should the neurological exam demonstrate focal neurologic recovery (i.e., awake, alert and oriented), the RA will send a Voalte message to survivor's bedside nurse [or other clinician known to the survivor] to confirm recovery of focal neurological status and to ask the survivor for permission to be contacted by our team to explain the study (either in person or over phone if the survivor is discharged before we are able to approach).

Medical and/or social work partners caring for CA survivors that may benefit from our study have volunteered to provide basic information of our study (the same information listed on our study flyer, which they will give to such survivors) and ask the patients for their permission to refer them to us through the Voalte messaging system.

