## 5. Subject Enrollment

We are requesting a waiver of consent for logging the clinical cardiac arrest variables for all cardiac arrest admissions. These variables are already listed in their electronic medical record, and the review of such records is for very limited information. Further, the variables are not sensitive in nature. We will collect such variables and log them on a hospital-based, secured data capture software (REDCap).

For survivors that meet criteria for our open pilot as discussed in section 4, once a potential survivor has been identified and approved by the clinical team, and has granted permission for us to contact them, a member of the study team will approach the survivor as soon as possible.

Survivors and caregivers that wish to participate will complete written informed consent. All potential participants will be given a paper informed consent form, a tablet to complete e-consent through REDCap, or will be emailed the consent form via REDCap depending on their preference. All participants will be given the opportunity to ask any questions. These discussions will cover the potential risks and benefits of participation, as well as information regarding who participants can contact for further questions. Potential participants will also be informed that participation is voluntary, that they can refuse to answer any

questions, and they can withdraw from the study at any time. They will be informed that refusal to participate in the study will in no way impact their own or their loved one's medical care.

Participants will be given the option to receive text messages with reminders to practice skills (active intervention only) as well as survey invitations, and study contact information (including that of the IRB) in case questions arise at a later time. The text messages will be sent via Twilio, a third party, Partners-approved, web service that integrates with REDCap to send survey invitations over SMS text messaging.

Once all questions have been answered, participants interested in participating will return a physical signed consent form or will sign virtually via e-consent. Study staff will keep all informed physical consent forms in a cabinet under lock and key.

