**All measures will be administered at both timepoints unless otherwise stated:**

- Demographics (baseline only)
- Charlson Comorbidity Index (baseline only)
- Barthel Index (survivor only)
- Modified Rankin Scale (survivor only)
- Mini Mental State Exam (survivor only; baseline only)
- Cerebral Performance Category Scale (survivor only)
- Telephone Interview for Cognitive Status (survivor only)
- Clinical Covariates Pre-test (survivor only)
- Clinical Covariates Post-test (survivor only)
- Hospital Depression and Anxiety Scale (HADS)
- Post-Traumatic Stress Disorder Checklist – 5
- The Cognitive and Affective Mindfulness Scale-Revised (CAMS-R)
- ENRICH Social Support Inventory
- Measure of Current Status Part A (MOCS-A)
- Mental Health Resource Usage
- Credibility and Expectancy Questionnaire (CEQ) (original measure administered at pre-test; measure was also adapted to be administered post-test to examine credibility and expectancy after having completed the program).
- Client Satisfaction Questionnaire (CSQ-3; post-test only)
- WHO Quality of Life-Brief
- Dyadic Relationship Scale
- Dyadic Coping Inventory
- Applied Mindfulness Scale
- Preparedness for Caregiving Scale (cargiver only)
- Meaning in Life Questionnaire
- 4 cardiac items from the Anxiety Sensitivity Index
- Gratitude Questionnaire Six Item Form

To understand the CA clinical characteristics of all admitted CA patients at MGH, we also request a waiver of consent to collect the following from the electronic medical record of all logged patients. These characteristics will also be logged for the open pilot patients:

- Cardiac arrest location
- Time until return of spontaneous circulation (ROSC)
- Initial cardiac arrest rhythm
- Age, sex

Each member of the dyad will receive up to \$60 in compensation (\$20 for baseline assessments and \$40 for post-test assessments). Payment will be made as gift cards.

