## 9. Statistical Analysis

For open pilot quantitative data, we will assess the feasibility benchmarks (recruitment, assessments, adherence, therapist fidelity) and acceptability benchmarks (satisfaction, credibility) (see **Table 1**) through frequencies and proportions. For qualitative data, we will examine exit interviews using thematic analysis. We will then conduct mixed methods analysis using an explanatory-sequential design, which allow us to integrate quantitative and qualitative data to refine the RT-CA manual and study procedures. We will use the exit interviews to explain the open pilot quantitative findings.

**Table 41** Feasibility and Acceptability Benchmarks.

Outcome	Benchmark
Feasibility (>70% Acceptable; >80% Excellent)	
Recruitment	% Eligible dyads who participate
Assessments	% Dyads with no measures missing
Adherence	% RT-CA dyads that complete 4/6 sessions
Therapist Fidelity	% RT-CA selected sessions (20%) (100% adherence on Fidelity Checklist)
Acceptability (>70% Acceptable; >80% Excellent)	
Treatment Acceptability	% RT-CA dyads score above midpoint on Client Satisfaction Questionnaire-3
Credibility and Expectancy	% RT-CA dyads score above midpoint on Credibility/Expectancy Questionnaire
Adverse Events	(Minimal/None)

For contextualizing the clinical cardiac arrest characteristics of our open pilot sample, we will conduct chi square and Wilcoxon rank sum tests for categorical and continuous variables to examine differences in our open pilot sample compared to all MGH cardiac arrest admissions, and all cardiac arrest admissions in the US as reported by the AHA.

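### Do the two projected sizes for the cardiac arrest record review (200-400 and 100-300) need to be reconciled before the plan can be used?

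*Combined protocol and SAP*

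**What the plan says.** Section 2 (Specific Aims and Objectives) defines Aim 2 as a medical record review "of all admitted cardiac arrest patients at MGH during the study period (N = 200-400"). Its purpose is to judge how well the open pilot sample represents cardiac arrest admissions at the hospital and in the United States.

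Section 3 (General Description of Study Design) describes a record review with the same population, site, period and purpose, run in parallel with the pilot. There the team will "maintain them in a study log (N = 100-300").

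Three other sections bear on who is in the log:

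- Section 4 (Subject Selection) describes a log "stored on REDCap of all CA survivors admitted to MGH during the study period". For patients who do not recover enough to join the pilot, it adds that "we will keep their basic clinical cardiac arrest characteristics in the admissions log for the duration of the study".
- Section 5 (Subject Enrollment) requests a "waiver of consent for logging the clinical cardiac arrest variables for all cardiac arrest admissions".
- Section 6 (Study Procedures), after the list of measures, says "we also request a waiver of consent to collect the following from the electronic medical record of all logged patients", and then: "These characteristics will also be logged for the open pilot patients".

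Section 9 (Statistical Analysis) plans chi-square and Wilcoxon rank sum tests "to examine differences in our open pilot sample compared to all MGH cardiac arrest admissions", and also compared with published national figures. It quotes no size for the log.

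**The concern.** Two sections give different projections for what appears to be one cohort. A reader cannot tell which is intended, because the protocol gives no admission rate or study duration from which either could be rebuilt. A final count of 100 to 199 would fit Section 3 but not Section 2. A count of 301 to 400 would fit Section 2 but not Section 3.

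Three things could be at stake. The records are to be reviewed without consent, so the expected number of patients is part of how large that request looks. A later report that sets the achieved log against the plan would have two reference figures. And if a precision or power argument rested on the log size, a twofold difference at the lower bound would matter.

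**Working it through.** **Step 1: is it one cohort or two?**

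| Feature | Section 2, Aim 2 | Section 3 |
|---|---|---|
| Population | all admitted cardiac arrest patients | all admitted cardiac arrest patients |
| Site and period | MGH, study period | MGH, study period |
| Purpose | representativeness of the pilot sample | the same, plus monitoring for eligibility |
| Projected N | 200-400 | 100-300 |

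The reference to survivors in Section 4 might suggest that the log is a smaller subset. It does not explain the gap. Section 3 says all admissions enter the log, Section 4 keeps patients who do not recover, and Section 6 logs the pilot patients too. No second log is described. It is one cohort.

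**Step 2: how far apart are the ranges?**

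- Lower bounds: 200 − 100 = 100, a ratio of 2.
- Upper bounds: 400 − 300 = 100, a ratio of 1.33.
- Midpoints: (200 + 400)/2 = 300 and (100 + 300)/2 = 200.
- Overlap: 200 to 300, a width of 100 out of 200 in each range, or half.

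Neither figure can be reproduced. The protocol states no error rate, power, effect size, admission rate or duration behind them.

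**Step 3: does either figure drive anything?**

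- *Who is logged.* All admissions, whatever their number.
- *Waiver.* Sections 5 and 6 define it by population (all admissions, all logged patients), with no numeric limit.
- *Benchmarks.* The feasibility and acceptability benchmarks in Section 9 concern pilot dyads and their sessions. None uses the log.
- *Tests.* Section 9 applies its tests to whatever data the log holds.

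**Step 4: would the log size change the comparison with hospital admissions in Section 9?**

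The comparison sets 5 pilot survivors (5 dyads, one survivor each) against N logged admissions. Assume a characteristic present in 50% of both groups, and ignore that the pilot patients are also in the log. The approximate 95% half-width for the difference is 1.96 × √(0.25/5 + 0.25/N). The normal approximation is rough with 5 patients, but it is enough to show which term dominates.

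| N logged | 0.25/5 + 0.25/N | Half-width (points) |
|---|---|---|
| 100 | 0.05250 | 44.9 |
| 200 | 0.05125 | 44.4 |
| 300 | 0.05083 | 44.2 |
| 400 | 0.05063 | 44.1 |

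From the smallest to the largest N in either range, the half-width moves by 44.9 − 44.1 = 0.8 points. The term 0.25/5 = 0.05 accounts for at least 95% of the variance (0.05/0.0525).

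**Step 5: the hospital against the United States.**

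Section 4 also mentions this comparison. If the hospital's admissions are treated as a sample, the half-width for a 50% characteristic is 1.96 × √(0.25/N): 9.8, 6.9, 5.7 and 4.9 points at N = 100, 200, 300 and 400. If the log is read as a complete count of the study period, as the protocol describes it, there is no sampling error and these figures do not apply. On either reading the precision follows from the count achieved, not from the projection.

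**The case for a change.** The strongest case for acting is that the contradiction is on the face of the current text, is not explained by any subset reading, and would cost almost nothing to remove. It also concerns records accessed without consent, where the protocol should give one answer on expected scale.

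The first part stands: these are two different projections of one quantity, and the protocol does not say which is meant. Their overlap does not reconcile them, although a final count between 200 and 300 would satisfy both.

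The consent argument is weaker. What the waiver request covers is clear, because it names the population and sets no limit. Only the expected volume is uncertain, and both ranges are of the same order. The variables are few: arrest location, time to return of circulation, initial rhythm, age and sex.

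Low cost does not make this a change to the plan. Aligning the figures would be good housekeeping at a future amendment, but no patient would be handled differently and no result would be computed differently.

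**Conclusion.** The discrepancy is confirmed, at 100 patients at each bound, and it is a clerical slip. Both ranges are unsupported projections of a count that will be complete by design. No eligibility rule, procedure, variable, benchmark, test or waiver limit depends on either. Over the whole span from 100 to 400, the precision of the comparison between pilot and hospital admissions changes by 0.8 points on a half-width of about 44 to 45.

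This rests on two readings of the text: that the log takes all admissions, as Sections 3 to 6 indicate, and that the waiver has no numeric cap, since none is stated. The half-widths also assume a 50% prevalence and independent groups. An analyst would report the number actually logged and proceed. No change to the plan follows.
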